10.3 Visit Windows for Safety Analyses

The table below presents the visits assigned for safety analyses corresponding to the range of treatment study days (window) during which an actual visit (scheduled or unscheduled) may occur. Note that the windows defined for statistical analysis are different from the ones defined in Protocol Section 9.

Visit windows for laboratory tests, vital signs, and for Columbia Suicide Symptoms and Signs Rating Scale (CSSRS):

Derived Visit	Target Study Day [1]	Window [2]
Baseline (for laboratory tests and vitals)	Day 1	Days <= 1
Baseline (for C-SSRS)	Screening (Visit 1)	NA
Visit 2 (for C-SSRS)	Day 1	Days = 1
Visit 3	Day 15	>= Day 2 to <= Day 22
Visit 4	Day 29	>= Day 23 to <= Day 36

Visit 5	Day 43	>= Day 37 to <= Day 50
Visit 6	Day 57	>= Day 51 to <= Day 64
Visit 7	Day 71	>= Day 65 to <= Day 78
Visit 8	Day 85	>= Day 79 to <= Day 92
Visit 9	Day 99	>= Day 93 to <= Day 106
Visit 10	Day 113	>= Day 107 to <= Day 128
Visit 11	Day 143	>= Day 129 to <= Day 173
Visit 12	Day 203	>= Day 174 to <= Day 233
Visit 13	Day 263	>= Day 234 to <= Day 314
Visit 14	Day 365	>= Day 315 to <= Day 410
3 Months after 1 Year Treatment	Day 456	>= Day 411 to <= Day 501
6 Months after 1 Year Treatment	Day 547	>= Day 502 to <= Day 592
9 Months after 1 Year Treatment	Day 638	>= Day 593 to <= Day 684
12 Months after 1 Year Treatment	Day 730	>= Day 685 to <= Day 775
15 Months after 1 Year Treatment	Day 821	>= Day 776 to <= Day 866
18 Months after 1 Year Treatment	Day 912	>= Day 867 to <= Day 957
21 Months after 1 Year Treatment	Day 1003	>= Day 958 to <= Day 1049
24 Months after 1 Year Treatment	Day 1095	>= Day 1050 to <= Day 1112
Visit 15 (14-day follow-up)	Day of the last dose of study	>= day of the last dose of study drug+14

	drug+14 days	
Termination Visit [3]	Termination Visit during treatment period	

[1] Relative to the date of the first dose of study drug. For example, Day 1 = the date of the first dose of study drug.

[2] The study days evaluated for windows of visits during treatment period are on or prior to the last dose day.

[3] For subjects who decide not to continue in the study at any time (i.e., eCRF check box for “Continuing” is answered ‘No’), the Termination Visit is performed (as per Protocol Section 9.1.14). This is available for entry at any time as a separate visit on eCRF. The study day for the termination visit will be assigned relative to the first dose of study drug.

Visit windows for ECG measurements:

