The following conventions will be used for the derived visits with respect to safety variables:

1. If more than one actual visit date (including the unscheduled visits) falls within the same window, the visit closest to the target study day will be considered for analysis.
2. If 2 actual visit dates within a window are at the same distance from the target study day, the later visit with non-missing data will be considered for analysis. If repeated measurements are all taken on the same day, then the last measurement will be used.
3. Values recorded at Termination Visit will be mapped to the derived visit based on the window where the actual visit date falls in per rules 1 and 2 above.
4. Given the rules for completing the Termination Visit on eCRF (as defined in Protocol Section 9.1.14), the results recorded at Termination Visit will be summarized in the safety tables at both derived visit based on rule 3 above and at Termination Visit.

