13.2 Analysis of Clinical Laboratory parameters

Individual laboratory values (hematology, chemistry, and urinalysis) will be listed by subject and summarized using descriptive statistics (mean, standard deviation, median, minimum, and maximum) by safety evaluable subgroups and by visit. Both SI and Conventional units will be used in reporting summary results.

Baseline measurement is defined as the last available measurement prior to dosing.

Post-baseline timepoints will be derived as per rules included in [Section 10.3](#).

Individual change from baseline (the last available measurement prior to dosing) in laboratory values will be calculated and summarized descriptively (mean, standard deviation, median, minimum and maximum) for each post-baseline visit. Summary results will be presented by post-baseline timepoints.

Shift tables from baseline to each post-baseline timepoint will be prepared for all laboratory assessments based on the categories of Low, Normal, and High (for numerical results) or Abnormal and Normal (for categorical results).

Overall summary tables for shift from normal/abnormal (low or high) baseline to normal or abnormal post-baseline accounting for all post-baseline results during study will also be prepared. For these summary tables both scheduled and unscheduled post-baseline visits will be considered and subjects will be counted as shift to post-baseline normal if they do not have any abnormal (High or Low) post-baseline results during the treatment period; and as shift to post-baseline abnormal they have at least one post-baseline abnormal (High or Low) post-baseline results.

The following abnormality categories will be derived to evaluate liver function test results:

- AST
 - $\geq 3 \times \text{ULN}$
 - $> 5 \times \text{ULN}$
 - $> 10 \times \text{ULN}$
- ALT
 - $\geq 3 \times \text{ULN}$
 - $> 5 \times \text{ULN}$
 - $> 10 \times \text{ULN}$
- Total Bilirubin
 - $> 1 \times \text{ULN}$
 - $> 1.5 \times \text{ULN}$
 - $\geq 2 \times \text{ULN}$
- Alkaline phosphatase
 - $> 2 \times \text{ULN}$
 - $> 3 \times \text{ULN}$

The number and percentage of subjects with clinical laboratory test values in each category for the laboratory tests listed above will be summarized by each timepoint (including baseline) and overall (ie, anytime post-baseline), and by safety evaluable subgroups.

Pregnancy test results will be listed by subject (females only) by visit.

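### The only laboratory shift table that uses every post-baseline result (SAP 13.2) merges Low and High, so results not selected for a visit window lose their direction in the shift summaries

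*SAP*

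**What the plan says.** SAP 13.2 plans two kinds of laboratory shift table.

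- **By timepoint.** The plan reads: "Shift tables from baseline to each post-baseline timepoint will be prepared for all laboratory assessments based on the categories of Low, Normal, and High". This three-way coding applies where the result is a number. On the timepoints, the section says "Post-baseline timepoints will be derived as per rules included in" SAP 10.3. Those windows cover study days "during which an actual visit (scheduled or unscheduled) may occur". The selection rule is: "If more than one actual visit date (including the unscheduled visits) falls within the same window, the visit closest to the target study day" is the one analysed. Note 2 to the window table limits on-treatment windows to days up to and including the last dose. The Visit 15 window opens 14 days after the last dose. Termination Visit results are summarised both under that label and in the window where they fall.
- **Overall.** "Overall summary tables for shift from normal/abnormal (low or high) baseline to normal or abnormal post-baseline accounting for all post-baseline results during study". On the visits used: "For these summary tables both scheduled and unscheduled post-baseline visits will be considered". On the outcome, a subject is counted "as shift to post-baseline abnormal they have at least one post-baseline abnormal (High or Low) post-baseline results". The matching definition of normal refers to results in the treatment period.

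SAP 13.2 also counts AST, ALT, total bilirubin and alkaline phosphatase above upper-limit multiples, by timepoint and at any time post-baseline. Individual values are listed by subject, and under SAP 15.1 the listings show scheduled and unscheduled visits.

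**The concern.** The two kinds of table each keep one of the two things a reader needs. The by-timepoint tables keep direction but take one visit per window. The overall table takes every result but drops direction. A result not selected for its window can reach only the overall table, where High and Low look the same.

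For many analytes, high and low are separate safety questions. DRESS includes eosinophilia in its name (Protocol Section 2), and three cases among 953 exposed subjects led to the close-monitoring plan in Protocol 4.5.1. SAP 8.2.2 collects a white count with differential. Apart from the liver tests, SAP 13.2 plans no laboratory summary that counts any post-baseline High separately from any post-baseline Low. For eosinophils, white cells and platelets, the report would therefore not show how many subjects were ever high, or ever low, on all the data.

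**Working it through.** The documents give no figure on this point. The check sets the rules against each other and enumerates their consequences.

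**1. What the overall table merges.** Take three baseline states and four post-baseline patterns, 3 × 4 = 12 combinations, and apply the SAP 13.2 rule.

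| Baseline | No abnormal | Low only | High only | Both |
|---|---|---|---|---|
| Low | Abn→Norm | Abn→Abn | Abn→Abn | Abn→Abn |
| Normal | Norm→Norm | Norm→Abn | Norm→Abn | Norm→Abn |
| High | Abn→Norm | Abn→Abn | Abn→Abn | Abn→Abn |

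The 12 combinations fall into 4 cells: Norm→Norm 1, Norm→Abn 3, Abn→Norm 2, Abn→Abn 6. Low-to-High sits with Low-to-Low and High-to-High. If the baseline wording means separate Low and High rows, there are 3 × 2 = 6 cells, but each post-baseline abnormal cell still pools low only, high only and both.

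**2. Whether unscheduled results reach the directional tables.** The 20 on-treatment laboratory windows in SAP 10.3 run from Day 2 to Day 1112 without a gap. Any unscheduled result in that span, up to the last dose day, is a candidate. Two examples for Visit 5 (target Day 43):

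- Unscheduled Day 44 (distance 1) against scheduled Day 41 (distance 2): the unscheduled result is used.
- Unscheduled Day 48 (distance 5) against scheduled Day 43 (distance 0): the unscheduled result is not used.

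**3. How often the rule passes an unscheduled draw over.** Protocol Section 9 allows ±2 days for Visits 3 to 10, so an on-time Visit 5 falls on Days 41–45. The analysis window is Days 37–50, which is 14 days. A draw on Days 37–40 (4 days) or 46–50 (5 days) is at least 3 days from target, so it always loses to an on-time Visit 5: 4 + 5 = 9 of 14 days.

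**4. Results after the last dose.** On-treatment windows end on the last dose day and Visit 15 opens at last dose + 14. Days +1 to +13 have no by-timepoint window unless the sample is recorded at the Termination Visit. Protocol 9.3 provides for unscheduled rash visits and for immediate discontinuation in some of them, so for-cause samples in this interval are foreseeable. The overall table could include them, although its reference to the treatment period in the normal category leaves this unclear.

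**5. Mixing in the merged cell (illustration only).** Scheduled post-baseline draws up to one year, plus follow-up, are Visits 3–10, 12, 13, 14 and 15: 8 + 3 + 1 = 12. Assume 2.5% chance results on each side per draw; this figure is not in the documents. The share of subjects with at least one chance-abnormal result is:

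- Independent draws: either direction 1 − 0.95^12 = 46%; one direction 1 − 0.975^12 = 26%.
- Fully correlated draws: 5% and 2.5%.

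The ranges are 5–46% and 2.5–26%. Independence gives the upper end. With Visit 15 left out (11 draws), the upper ends are 43% and 24%. These figures describe mixing of directions in scheduled data. They do not measure how many unscheduled results are lost.

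**The case against.** Several stronger readings are tempting, and the documents do not support them.

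- *The overall table is the only one using unscheduled results.* It is not. SAP 10.3 admits unscheduled visits to the windows, and one can displace a scheduled visit. What is unique to the overall table is that it uses all results.
- *A Low-to-High change is reported as no shift.* The SAP does not use that label. Such a subject is counted as post-baseline abnormal; the difficulty is the shared cell. The table templates are in separate documents not available here.
- *Liver safety is obscured.* The four liver tests have any-time, high-side counts.
- *Eosinophilia will mostly appear on unscheduled draws.* No document says so, and Visits 3 to 10 carry safety bloods every two weeks.

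The wider defence is that the study is single-arm and descriptive (SAP 10.1), that the overall table supplements directional ones, and that listings keep every value. In addition, abnormalities suggesting organ toxicity or needing active management are to be recorded as adverse events (Protocol 10.1.5, under abnormal laboratory values), so they reach the TEAE tables by preferred term.

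This defence limits the consequence without removing the gap. Adverse event capture depends on investigator judgement. By-subject listings for a study meant to expose at least 1,000 subjects for 6 months do not replace a count. SAP 13.4 already counts vital signs by direction over scheduled and unscheduled measurements, so the SAP itself treats this as the useful summary.

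**Conclusion.** The point holds as a minor reporting weakness. The one shift table built on all post-baseline results does not separate Low from High. Results that lose the closest-to-target contest, or that fall 1–13 days after the last dose outside a Termination Visit, can be absent from every directional shift table. The merging follows from the SAP's own definition and holds under either reading of its baseline wording. The 9-of-14-day figure assumes Visit 5 took place within its protocol window.

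The number of results affected cannot be estimated, because the documents give no rate of unscheduled draws. The effect falls on haematology and non-liver chemistry. No test or decision rule depends on this table, so no conclusion of the study is at risk. What changes is whether the report can say how many subjects were ever high or ever low in eosinophils, white cells or platelets.

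**What to change.** In SAP 13.2, replace the overall table for numerical tests with baseline Low/Normal/High against two outcomes:

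- (a) any post-baseline High, classified by the subject's highest value;
- (b) any post-baseline Low, classified by the lowest value.

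Use all scheduled and unscheduled results, and let a subject with both count in both. Keep normal/abnormal for categorical tests. State one period for the table, including whether results after the last dose count, because the current text mentions both the study and the treatment period.

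The change needs no new data or visits. It costs one extra set of columns and a revised table template and program, before database lock.

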After initiating treatment with YKP3089 for two weeks at 12.5 mg and then for two weeks at 25mg YKP3089, subjects taking phenytoin or phenobarbital will titrate YKP3089 upward at a rate of 50mg every other week to a target dose of 200mg/day. This titration is appropriate for this portion of the study because of the known interactions between YKP3089 200mg and phenytoin and phenobarbital. Titrating by 50mg of YKP3089 every other week to steady state will allow better understanding of the clinical impact of any interaction and allow for dosage adjustment of phenytoin or phenobarbital.

Subjects taking concomitant AEDs other than phenytoin or phenobarbital will titrate YKP3089 upward at the same rate to a target dose of 200mg/day.

After reaching a target dose of 200mg, all subjects will be allowed to titrate up to a maximum dose of 400mg/day of YKP3089. A maximum dose of 400mg/day is justified by the additional efficacy seen in the subjects randomized to 400mg/day in the completed dose response study. Seizure free rate effect size in this group approached 20% during the maintenance phase.

4.6 **Potential Risks and Benefits**

Cumulatively, 953 subjects have been exposed to YKP3089 in a total of 14 Phase 1 and 3 Phase 2 clinical studies.

The potential risks in this study includes,

1. Phenytoin dose related toxicity
2. Risk of phenytoin hypersensitivity syndrome
3. Phenobarbital dose related toxicity
4. Rash / hypersensitivity related to YKP3089 exposure
5. DRESS syndrome related to YKP3089 exposure
6. YKP3089 dose related toxicities

Uncontrolled partial epilepsy is a life threatening disease with significant morbidity and elevated standard mortality rates.

The early signs and symptoms associated with hypersensitivity reaction that may progress to DRESS are readily identifiable by patients and clinicians. When detected and adequately managed, progression to DRESS can be prevented or reversed. The potential benefits of YKP3089 include significant partial seizure frequency reduction and substantial seizure free rates (~18%) in patients who continue to suffer seizures despite history of treatment with multiple AEDs. The current benefit/risk profile in conjunction with the risk minimization measures support the enrollment of partial epilepsy patients into this open-label study to assess the profile of YKP3089 as a potential antiepileptic drug

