1 REVISION HISTORY

Versi on	Date	Author	Description
1.0	25Sep2017	QDS	Based on Protocol Amendment 3
2.0	19Jun2018	QDS	Updated per Protocol Amendment 4 and additional requests from SKLSI after meeting with FDA
3.0	26Jul2018	QDS	Clarifications for Physical Exam, C-SSRS visit windows. Updated definition for duration of epilepsy. Removed analyses for overall compliance. Administrative changes for subjects disposition, clinical laboratory tests, vital signs analyses
4.0	23Aug2018	QDS	Removed reference to Screen Failures as an analysis population. Removed all analyses by country and region. PK Section: AED plasma concentration analysis will be based on Central Lab results Included Study Assessment Flowchart from Protocol Amendment 4 in Appendix 1
5.0	05Sep2018	QDS	Updated analyses for LFTs to include all baseline values (ie, not restricted to normal baseline)

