8.2.2 Other Safety Measures

Concomitant medications and concomitant procedures will be recorded on the Prior and Concomitant eCRF and Concomitant Procedures eCRF, respectively.

Concomitant AED administration since last visit will be recorded on the eCRF page.

Vital signs will be recorded on the Vital Signs eCRF. These data will include blood pressure, heart rate (supine for 5 minutes), temperature, respiratory rate, and weight.

Physical examinations will be recorded on the Physical Exam eCRF. These data will include Body System, normal/abnormal indication, and a description of the abnormality.

Routine 12-lead ECGs will be performed periodically during the study. Parameters including Heart rate, PR interval, QRS interval, RR interval, QT interval, and QTcF will be measured. These results will be recorded on the eCRF.

A brief neurologic evaluation examination will be made and recorded on the eCRF.

Clinical laboratory evaluations will be collected and returned electronically and not entered on an eCRF. Clinical Laboratory Evaluations will include the following:

- Hematology: hemoglobin, hematocrit, white blood count with differential, RBC count, platelet count, and calculated indices.
- Serum chemistry: blood urea nitrogen (BUN), calcium, chloride, creatinine, glucose, total bilirubin, direct bilirubin, alkaline phosphatase, aspartate transaminase (AST), alanine aminotransferase (ALT), total protein, albumin, globulin, sodium, potassium, phosphorus, and glucose. Serum creatinine will be used to calculate the creatinine clearance.
- Urinalysis: pH, specific gravity, protein, glucose, ketone, bilirubin, blood, nitrite, urobilinogen, and microscopic examination
- Pregnancy Tests – All females of child-bearing potential will undergo a serum pregnancy test for β -hCG (β -human chorionic gonadotropin).

All safety laboratory samples will be analyzed by a central laboratory.

The follow-up version of the Columbia Suicide Rating Scale (C-SSRS) will be assessed at Visit 2 and all subsequent visits throughout the study and entered on the eCRF.

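### No planned liver summary counts subjects with AST or ALT ≥3×ULN and total bilirubin ≥2×ULN on the same draw

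*SAP*

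**What the plan says.** The liver analysis is in SAP 13.2. It opens with "The following abnormality categories will be derived to evaluate liver function test results" and gives four separate lists: AST and ALT (each ≥3, >5 and >10×ULN), total bilirubin (>1, >1.5 and ≥2×ULN) and alkaline phosphatase (>2 and >3×ULN). The tabulation rule is "The number and percentage of subjects with clinical laboratory test values in each category for the laboratory tests listed above", and these counts "will be summarized by each timepoint (including baseline) and overall (ie, anytime post-baseline), and by safety evaluable subgroups". No category combines two analytes, and AST and ALT are not merged into an either/or category.

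The other laboratory summaries in 13.2 also take one analyte at a time: descriptive statistics, change from baseline, an overall normal/abnormal shift, and by-visit shifts, of which the SAP says "Shift tables from baseline to each post-baseline timepoint will be prepared for all laboratory assessments based on the categories of Low, Normal, and High". I found no combined transaminase and bilirubin criterion elsewhere in the SAP or the protocol. SAP 16 records only that liver function analyses were added to what the protocol specified.

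Two further provisions matter. SAP 13.2 also says "Individual laboratory values (hematology, chemistry, and urinalysis) will be listed by subject", and SAP 15.1(b) has by-subject listings run in date order with scheduled and unscheduled visits. SAP 8.2.2 puts all four analytes in one serum chemistry panel from a central laboratory.

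**The concern.** A transaminase elevation and a bilirubin elevation in one subject on one day is a different finding from the same two elevations in two subjects, or in one subject months apart. Separate rows cannot tell these apart. One subject with both, and two subjects with one each, add the same 1 to the transaminase row and 1 to the bilirubin row. The any-time row carries no date, so it cannot show that two elevations came from one sample.

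Long-term safety is a stated objective (Protocol 5), and Protocol 4.6 lists "DRESS syndrome related to YKP3089 exposure" among the risks. Protocol 4.5.1 reports three such cases among 953 exposed subjects. The sponsor chose to add liver thresholds and, in SAP version 5.0, to include subjects whatever their baseline liver values. At stake is whether the report can state how many subjects crossed both thresholds together. As planned, a reader who asks that question must search the listings.

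**Working it through.** The plan gives no figure on this point to reproduce. SAP 9.1 states that there was no formal sample size estimation. The check is what the planned rows can reveal about the joint count.

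**Inputs.** N = 1,000 is the minimum number to be exposed for 6 months (Protocol 6.1, SAP 9.1). The thresholds are those of SAP 13.2. The row counts below are assumptions, since the documents give none.

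**Formulas.** Let A and L be the any-time counts for AST and ALT ≥3×ULN, and B the count for bilirubin ≥2×ULN.
- Subjects with AST or ALT ≥3×ULN: T lies between max(A, L) and A + L.
- Subjects with both a transaminase and a bilirubin elevation at any time: between max(0, T + B − N) and min(T, B).
- The same-draw count has the same upper limit. Its lower limit is 0, because elevations at any time need not share a draw.

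| ALT ≥3× | AST ≥3× | Bilirubin ≥2× | AST or ALT ≥3× | Joint count | Joint % of 1,000 |
|---|---|---|---|---|---|
| 5 | 3 | 2 | 5 to 8 | 0 to 2 | 0 to 0.2 |
| 10 | 8 | 5 | 10 to 18 | 0 to 5 | 0 to 0.5 |
| 20 | 15 | 10 | 20 to 35 | 0 to 10 | 0 to 1.0 |
| 10 | 8 | 0 | 10 to 18 | 0 | 0 |

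For the second line, T runs from max(8, 10) = 10 to 8 + 10 = 18, and the joint count runs from 0 to min(18, 5) = 5. The planned rows therefore give only a ceiling. They settle the same-draw count when the bilirubin row, or both transaminase rows, are zero.

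**What an exact count adds.** If the joint count were 0 in 1,000, the one-sided exact 95% upper bound would be 1 − 0.05^(1/1000) = 0.0030, or 0.30%.

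**Effort of using the listings instead.** Appendix 1 of the SAP schedules chemistry at Visits 1, 3 to 10, 12, 13 and 14, which is 1 + 8 + 3 = 12 draws to Day 365. A subject followed for 6 months (6 × 30.4 = 182 days, before Visit 12 on Day 203) has 9. For 1,000 subjects and four analytes that is 9 × 1,000 × 4 = 36,000 values at 6 months, or 12 × 1,000 × 4 = 48,000 if all complete year one, before unscheduled draws.

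**Which samples count.** The overall shift tables in SAP 13.2 and the vital-sign criteria in SAP 13.4 say expressly that unscheduled values are used. The any-time liver count does not say so. Under SAP 10.3 the treatment windows end on the last dose day and the Visit 15 window starts 14 days later, so a draw on days 1 to 13 after the last dose falls in no window.

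**The case against.** The strongest reply is that nothing is lost. The listings hold every value in date order, so a subject with both elevations appears in a planned output. The data come electronically from one laboratory, and the count can be produced at any time without affecting another result. This stands, and it limits the point to a missing count and flag. The SAP does plan a list of abnormal ECG results (13.3), but nothing similar for liver tests.

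A second route is adverse event reporting. Protocol 10.1.5 asks for a laboratory abnormality to be recorded as an adverse event if it suggests organ toxicity or needs active management, and serious events and those leading to discontinuation are listed (SAP 13.1). This depends on investigator reporting and does not replace a count against fixed thresholds.

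Third, the by-visit tables keep the draw closest to the target day, from which a reader might infer that peak values drop out. The any-time count largely answers that. What remains is that its text does not name unscheduled draws.

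Fourth, table templates are kept in separate documents (SAP 4) that I have not seen. If they contain a combined row, the sponsor need only cite it. SAP 13.2 does not call for one.

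**Conclusion.** The point holds as a gap in the planned summaries. Outside cases such as a zero bilirubin row, the plan cannot state how many subjects had AST or ALT ≥3×ULN with bilirubin ≥2×ULN on one draw. On assumed counts in 1,000 subjects the uncertainty is 0 to 2, 0 to 5 or 0 to 10 subjects. The structural conclusion does not depend on those counts; only the width of the range does. This is a low-cost improvement to a descriptive safety report and does not invalidate any planned result.

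Three stronger readings are not supported.
- A reader might infer that such cases would be missed. The listings show them, so they are unflagged, not absent.
- A reader might infer that a single joint case would itself be a signal. If each elevation occurred in 1% of 1,000 subjects independently (assumed rates), the expected joint number is 1,000 × 0.01 × 0.01 = 0.1, and the chance of at least one is 1 − exp(−0.1), about 10%. Independence is also doubtful for analytes from the same organ. One case calls for review and no more.
- A reader might infer that the separate rows will be inflated by benign enzyme rises on background drugs, or that version 5.0 made matters worse by including all baselines. The documents say nothing on the first. On the second, the change widens capture, and baseline is itself a tabulated timepoint.

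**What to change.** Add to the liver table in SAP 13.2 one any-time post-baseline row, overall and by safety evaluable subgroup: AST or ALT ≥3×ULN together with total bilirubin ≥2×ULN on the same sample date, split by alkaline phosphatase ≤2×ULN or >2×ULN on that date. State that it uses all scheduled and unscheduled post-baseline samples, whether or not they fall in an analysis window. Add a short listing of the subjects in the row, with the four values, the sample date and the baseline values.

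All cut-offs are already in the SAP and all four analytes come from one panel, so no visit, sample or clinical procedure changes. The cost is one extra row and one listing to program and validate.
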